#### **10.2.5.1. Treatment Week 16 (Visit T4.1; ±3 days)**

*Patients on simvastatin 40 mg/day will be scheduled for the additional Visit T4.1 for clinical safety laboratory evaluations specifically to monitor changes in creatine phosphokinase (CPK)*

*and liver function tests (LFTs). Should changes be noted, the procedures described in Section 11.1.6.3.1 will apply.*

- *Concomitant and prohibited medication review (ongoing)*
- *Assess AEs, including muscle-related AEs (ongoing)*
- *Clinical laboratory evaluations:*
  - *Hematology, blood chemistry, and urinalysis*
- *Conduct diet and exercise counseling*

#### **10.2.5.2. Treatment Week 20 (Visit T4.2; ±3 days)**

*Patients on simvastatin 40 mg/day will be contacted by telephone for the additional Visit T4.2*

- *Concomitant and prohibited medication review (ongoing)*
- *Assess AEs, including muscle-related AEs (ongoing)*

#### **10.2.6. Treatment Week 24 (Visit T5; ± 7 days)**

If the patient is withdrawing early from the study at this visit, proceed to [Section 10.2.8](#) for the list of the required assessments.

If the patient is withdrawing from IMP treatment at this visit, proceed to Section 10.2.8 for the list of the required assessments. The patient will be asked to continue to be followed for safety using the protocol-specified visit schedule. If the patient consents for follow-up, schedule the next protocol-specified visit.

Patients who do not provide consent to continue to return to the clinic for safety assessments after withdrawing from IMP treatment will be asked to participate in phone calls from the site at protocol-specified visits, or at a minimum at 52 weeks, to inquire about the patient's current health status and collect information on AEs (eg, recent procedures, hospitalizations, and if the patient has died, the cause of death). If the patient consents for telephone contacts, schedule the next protocol-specified visit.

Patients will undergo the following assessments and procedures at Week 24 (Visit T5):

- Concomitant and prohibited medication review (ongoing)
- Assess AEs, including muscle-related AEs (ongoing)
- Weight
- Vital signs
- Clinical laboratory evaluations:
  - Hematology, blood chemistry, and urinalysis
  - Basic fasting lipids (TC, calculated LDL-C, HDL-C, non-HDL-C, and TG)
  - apoB
  - hs-CRP

- PK sample (*patients randomized after Protocol Amendment 3 and subsequent amendments are excluded from PK sampling*)
- Reserve sample
- Conduct diet and exercise counseling
- Return of IMP; assessment and recording of IMP compliance
- IWRS contact to obtain the MED ID number for IMP
- Dispense IMP
- Schedule next visit

Note: If this visit is being conducted at the site for patients who have consented to be followed for safety assessments, *including basic fasting lipids*, after withdrawing from IMP treatment, all assessments except for those procedures pertaining to apoB, hs-CRP, PK samples, reserve samples, and IMP (IMP dispensing, IMP compliance, IMP accountability) management should be completed.

Note: If this visit is being conducted by telephone contact for patients who have consented to be followed by phone for safety assessments after withdrawing from IMP treatment, collect information as reported by the patient regarding AEs, *concomitant medications*, and current health status.

#### **10.2.6.1. Treatment Week 28 (Visit T5.1; ±7 days)**

*Patients on simvastatin 40 mg/day will be scheduled for the additional Visit T5.1 for clinical safety laboratory evaluations specifically to monitor changes in CPK and LFTs. Should changes be noted, the procedures described in Section 11.1.6.3.1 will apply.*

- *Concomitant and prohibited medication review (ongoing)*
- *Assess AEs, including muscle-related AEs (ongoing)*
- *Clinical laboratory evaluations:*
  - *Hematology, blood chemistry, and urinalysis*
- *Conduct diet and exercise counseling*

#### **10.2.6.2. Treatment Week 32 (Visit T5.2; ±7 days)**

*Patients on simvastatin 40 mg/day will be contacted by telephone for the additional Visit T5.2*

- *Concomitant and prohibited medication review (ongoing)*
- *Assess AEs, including muscle-related AEs (ongoing)*

#### **10.2.7. Treatment Week 36 (Visit T6; ± 7 days)**

If the patient is withdrawing early from the study at this visit, proceed to [Section 10.2.8](#) for the list of the required assessments.

If the patient is withdrawing from IMP treatment at this visit, proceed to [Section 10.2.8](#) for the list of the required assessments. The patient will be asked to continue to be followed for safety using the protocol-specified visit schedule. If the patient consents for follow-up, schedule the next protocol-specified visit.

Patients who do not provide consent to continue to return to the clinic for safety assessments after withdrawing from IMP treatment will be asked to participate in phone calls from the site at protocol-specified visits, or at a minimum at 52 weeks, to inquire about the patient's current health status and collect information on AEs (eg, recent procedures, hospitalizations, and if the patient has died, the cause of death). If the patient consents for telephone contacts, schedule the next protocol-specified visit.

Patients will undergo the following assessments and procedures at Week 36 (Visit T6):

- Concomitant and prohibited medication review (ongoing)
- Assess AEs, including muscle-related AEs (ongoing)
- Weight
- Vital signs
- Clinical laboratory evaluations:
  - Hematology, blood chemistry, and urinalysis
  - Basic fasting lipids (TC, calculated LDL-C, HDL-C, non-HDL-C, and TG)
- Conduct diet and exercise counseling
- Return of IMP; assessment and recording of IMP compliance
- IWRS contact to obtain the MED ID number for IMP
- Dispense IMP
- Schedule next visit

Note: If this visit is being conducted at the site for patients who have consented to be followed for safety assessments, *including basic fasting lipids*, after withdrawing from IMP treatment, all assessments except for those procedures pertaining to IMP management (IMP dispensing, IMP compliance, IMP accountability) should be completed.

Note: If this visit is being conducted by telephone contact for patients who have consented to be followed by phone for safety assessments after withdrawing from IMP treatment, collect information as reported by the patient regarding AEs, *concomitant medications*, and current health status.

#### **10.2.8. Treatment Week 52 (Visit T7; ± 7 days)**

Patients will undergo the following assessments and procedures at Week 52 (Visit T7), when completing an End of Study (EOS) visit, withdrawing from study (early withdrawal), or withdrawing from IMP treatment:

Patients will undergo the following assessments and procedures at Week 52 (Visit T7):

- Concomitant and prohibited medication review (ongoing)
- Assess AEs, including muscle-related AEs (ongoing)
- PE
- Weight
- 12-Lead ECG
- Vital signs
- Clinical laboratory evaluations:
  - Hematology, blood chemistry, and urinalysis
  - Basic fasting lipids (TC, calculated LDL-C, HDL-C, non-HDL-C, and TG)
  - apoB
  - HbA1C
  - hs-CRP
  - PK sample (*patients randomized after Protocol Amendment 3 and subsequent amendments are excluded from PK sampling*)
  - Reserve sample
- Return of IMP; assessment and recording of IMP compliance
- Complete study status in IWRS (ie, early withdrawal or completed study)
- *Review and offer the open-label extension study (Study 1002-050) to the patient*

Note: For patients who withdraw from IMP treatment:

- *Capture the reason for withdrawing from IMP treatment and record on the eCRF*
- Determine whether the patient will or will not consent for follow-up visits through study completion
- If the patient provides consent to continue to be followed for safety assessments per the protocol visit schedule, schedule follow-up visits as they would have occurred if the patient were continuing in the study and complete the visit required procedures listed in the appropriate visit specific section within **Section 10** and **Appendix 1**. No further IMP will be dispensed for patients who withdraw from IMP treatment.
- If the patient does not provide consent to be followed for safety assessments per the protocol (either by returning to clinic or by phone), this visit (Visit T7) will be considered the EOS/Early Withdrawal from study visit and no further visits will be scheduled.

Note: If this visit is being conducted at the site for patients who have consented to be followed for safety assessments, *including basic fasting lipids*, after withdrawing from

IMP treatment, all assessments except for those procedures pertaining to apoB, hs-CRP, PK samples, reserve samples, and IMP (IMP dispensing, IMP compliance, IMP accountability) management should be completed.

Note: If this visit is being conducted by telephone contact for patients who have consented to be followed by phone for safety assessments after withdrawing from IMP treatment, collect information as reported by the patient regarding AEs, *concomitant medications*, and current health status.

## 10.3. Subject Withdrawal Criteria

### 10.3.1. Early Withdrawal from the Study

Patients must remain in the study until the last scheduled visit at Week 52 (Visit T7) to be considered as having completed participation in the study.

Patients who withdraw from IMP prior to Week 52 (Visit T7) for any reason will be asked to continue to be followed for safety assessments, *including basic fasting lipids*, at clinic visit following the protocol-specified visit schedule (see [Appendix 1](#)). The patient must provide consent to be followed in the study after withdrawing from IMP treatment. Protocol procedures to be completed for patients who consent will include those specified at each visit as noted in Schedule of Events (see [Appendix 1](#)).

*Patients who temporarily withdraw from IMP prior to Week 52 (Visit T7) for any reason may restart IMP providing that 1) the patient and the investigator are in agreement regarding this course of action, 2) the patient has been off of IMP for 4 weeks or less; and 3) IMP can be started as soon as possible. For cases where the patient has been off of IMP for more than 4 weeks, the investigator must contact the medical monitor for approval prior to restarting IMP.*

Patients who do not provide consent to continue to return to the clinic for safety assessments will be asked to participate in phone calls from the site at protocol-specified visits (see [Appendix 1](#)), or at a minimum at 52 weeks, to collect information on AEs, *concomitant medications*, and current health status. The patient must provide consent to be contacted by phone by site personnel for the purposes of assessing current AEs and current health status.

The patient's decision to participate in the clinical study is voluntary. Patients may refuse to continue in the study and/or withdraw from participation in this study at any time, for any reason, specified or unspecified, and without penalty or loss of benefits to which the patient is otherwise entitled.

It is the right and duty of the Investigator to interrupt the treatment of any patient whose health or well-being may be threatened by continuation in this study. Such patients should be withdrawn from the study and should not be continued under a modified regimen.

Patients who are withdrawn from the study may not re-enter. The reasons for withdrawal from this study may include:

- Patient's withdrawal of consent
- Failure to comply with the protocol
- Lost to follow-up

- Illness, condition, or procedural complication (including AEs) affecting the patient's ability to participate or requiring prohibited medication
- The Sponsor or Investigator terminates the study
- In the Investigator's judgment, it is deemed in the best interest of the patient to discontinue his/her participation in the study
- Any other reason

If a patient is lost to follow-up, every reasonable effort must be made by the clinical site personnel to contact the patient and determine the reason for discontinuation/withdrawal. The measures taken to follow-up must be documented.

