#### **10.2.3. Treatment Week 4 (Visit T2; ± 3 days)**

If the patient is withdrawing early from the study at this visit, proceed to [Section 10.2.8](#) for the list of the required assessments.

If the patient is withdrawing from IMP treatment at this visit, proceed to [Section 10.2.8](#) for the list of the required assessments. The patient will be asked to continue to be followed for safety using the protocol-specified visit schedule. If the patient consents for follow-up, schedule the next protocol-specified visit.

Patients who do not provide consent to continue to return to the clinic for safety assessments after withdrawing from IMP treatment will be asked to participate in phone calls from the site at protocol-specified visits, or at a minimum at 52 weeks, to inquire about the patient's current health status and collect information on AEs (eg, recent procedures, hospitalizations, and if the

patient has died, the cause of death). If the patient consents for telephone contacts, schedule the next protocol-specified visit.

Patients will undergo the following assessments and procedures at Week 4 (Visit T2):

- Concomitant and prohibited medication review (ongoing)
- Assess AEs, including muscle-related AEs (ongoing)
- Weight
- Vital signs
- Clinical laboratory evaluations:
  - Hematology, blood chemistry, and urinalysis
  - Basic fasting lipids (TC, calculated LDL-C, HDL-C, non-HDL-C, and TG)
- Conduct diet and exercise counseling
- Return of IMP; assessment and recording of IMP compliance
- Return IMP container from Visit T1 to patient for continued dosing and provide dosing instruction
- Schedule next visit

*Note: If this visit is being conducted at the site for patients who have consented to be followed for safety assessments, including basic fasting lipids, after withdrawing from IMP treatment, all assessments except for those procedures pertaining to IMP management (IMP dispensing, IMP compliance, IMP accountability) should be completed.*

*Note: If this visit is being conducted by telephone contact for patients who have consented to be followed by phone for safety assessments after withdrawing from IMP treatment, collect information as reported by the patient regarding AEs, concomitant medication, and current health status.*

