#### **11.1.6.3.1. Monitoring and Management of Elevated Liver Function Tests**

If at any time after randomization a patient experiences a new ALT and/or AST  $>3 \times$  ULN, the patient will undergo repeat confirmatory LFT assessment as soon as is reasonably possible, preferably within 3 to 7 days of the laboratory result becoming available.

Repeat LFT assessment will include: 1) measurement of ALT, AST, alkaline phosphatase, total and direct bilirubin, prothrombin time (PT)/international normalized ratio (INR), eosinophil count, CK, antihepatitis A virus (total), HBsAg (confirmation of screening measurement), HCV (confirmation of screening measurement), and anti-cytomegalovirus/immunoglobulin M; 2) history of concomitant medication use; 3) history of exposure to environmental chemical agents, including ethanol; and 4) query for related symptoms. Additionally, further testing such as liver ultrasound or MRI scanning may be warranted to rule out additional pathology depending on clinical presentation and should be discussed with the Sponsor personnel or the authorized Medical Monitor.

- If repeat LFT assessment confirms ALT and/or AST  $>3 \times$  ULN, consideration should be given to withdrawing the patient and administering no further doses of study drug. At the investigator's discretion, study drug may be interrupted and the patient rechallenged with study drug after LFTs have returned to baseline levels.
- If repeat LFT assessment confirms ALT and/or AST  $>5 \times$  ULN, patient should be withdrawn from IMP treatment, but will be asked to continue to be followed for safety using the protocol-specified visit schedule (see [Appendix 1](#)).

- If repeat LFT assessment confirms ALT and/or AST  $>3 \times$  ULN in addition to any of the following, the patient should be given no further IMP treatment, but will be asked to continue to be followed for safety using the protocol-specified visit schedule (see [Appendix 1](#)):
  - TB  $>2 \times$  ULN  
*Note: In the case of patients with Gilbert's disease, TB will be fractionated and the determination of  $2 \times$  ULN will be based upon direct (conjugated) bilirubin.*
  - INR  $>1.5 \times$  ULN (unless the patient is on stable dose of anticoagulation medication)
  - Appearance or worsening of right upper abdominal discomfort, anorexia, fatigue, nausea, vomiting, fever, rash, or eosinophilia

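### Protocol 10.3.1 makes a health-related treatment interruption trigger withdrawal from the study, against its own follow-up and restart rules and the IMP stop-or-hold rules in 11.1.6.3.1 to 11.1.6.3.4

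*Protocol*

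**What the plan says.** Protocol 10.3.1 gives the investigator the right and duty to "interrupt the treatment of any patient whose health or well-being may be threatened by continuation in this study". It continues: "Such patients should be withdrawn from the study and should not be continued under a modified regimen". The following paragraph opens: "Patients who are withdrawn from the study may not re-enter".

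Earlier in the same section, patients who come off IMP before Week 52 "for any reason will be asked to continue to be followed for safety assessments", subject to consent. Patients who stop IMP temporarily "for any reason may restart IMP providing that" patient and investigator agree, the gap is 4 weeks or less and dosing can resume promptly. A longer gap needs the medical monitor's approval.

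The visit sections handle stopping IMP separately from leaving the study. At Week 4, for example, a patient stopping IMP has the end-of-treatment assessments and then: "The patient will be asked to continue to be followed for safety using the protocol-specified visit schedule". Section 11.1.6.3.1 adds, for confirmed ALT or AST above 3 × ULN, that "study drug may be interrupted and the patient rechallenged with study drug after LFTs have returned to baseline levels".

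The list of reasons for leaving the study, also in 10.3.1, has its own entry for cases where, in the investigator's judgment, "it is deemed in the best interest of the patient to discontinue his/her participation in the study".

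**The concern.** A health-related interruption falls under several instructions that cannot all be followed. One ends participation for good. The others stop or pause the drug, keep the patient on the visit schedule and, in some cases, allow dosing to resume. The protocol states no order of precedence among its own sections.

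The primary objective is long-term safety, and the patients concerned are those taken off drug for a safety reason. A site following the sentence may stop collecting scheduled data on them and will not restart IMP. Another site may record the same event as an IMP stop only. SAP 5.2.3 tabulates study withdrawal and IMP withdrawal by reason, so that table would partly reflect how each site read the sentence.

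**Working it through.** The plan gives no figure to reproduce. The check sets the rules side by side and then bounds the data at risk for one patient.

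**Step 1. Compare the rules.**

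| Confirmed event | Specific rule | 10.3.1 sentence read literally |
|---|---|---|
| ALT/AST > 5 × ULN (11.1.6.3.1) | Stop IMP, stay on visit schedule | Leave study, no re-entry |
| ALT/AST > 3 × ULN (11.1.6.3.1) | Consider withdrawing the patient (from what is not stated), or interrupt and rechallenge | Leave study, rechallenge closed |
| eGFR falling to 15 mL/min/1.73 m², or acute renal failure (11.1.6.3.2; no confirmation step) | Stop IMP, stay on visit schedule | Leave study, no re-entry |
| Hgb < 8 g/dL (11.1.6.3.3) | Stop IMP, weekly Hgb, stay on visit schedule | Leave study, no re-entry |
| CK > 5 × ULN with symptoms (11.1.6.3.4) | Hold IMP; resumption possible | Leave study, resumption closed |
| CK > 10 × ULN (11.1.6.3.4) | Withdrawn, no more drug; IMP not named, but the closing bullet asks for follow-up after IMP withdrawal | Leave study, no re-entry |

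**Step 2. See what other sections recover.**

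- Protocol 10.3.2 requires the early-withdrawal procedures for anyone who withdraws or is removed, and asks for every effort to get each patient through all visits. Its specific request for later visits or calls is addressed to patients who choose to leave or who leave all aspects of the study, so it does not plainly reach those the investigator removes. It does not reopen restart.
- Protocol 11.2.6 continues the assessments and tests relevant to the causal event until it resolves or stabilizes.
- Protocol 11.3 collects SAEs to 30 days after study discontinuation.
- The early-withdrawal visit (Protocol 10.2.8) collects laboratory tests, lipids, vital signs and ECG.
- SAP 3.2.1 counts TEAEs only to 30 days after last dose, and SAP 5.4.5 summarizes only treatment-emergent adjudicated endpoints. Most later events of these kinds would not be summarized anyway.

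Not recovered with certainty: later scheduled safety laboratory tests unrelated to the causal event, which SAP 5.4.6 would use because its AESI laboratory summary takes all post-baseline values; later vital signs and lipids; and new non-serious adverse events within 30 days of last dose.

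**Step 3. Bound the gap per patient.** SAP 5.1 windows in study days: Week 4 = 2–43, Week 8 = 44–71, Week 12 = 72–127, Week 24 = 128–211, Week 36 = 212–309, Week 52 = 310 onward. Assumptions: earlier visits attended on target days, the early-withdrawal visit done on the removal day and slotted by study day, and no later contact.

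| Day of removal | Analysis visits left empty | Count of 6 |
|---|---|---|
| 2–43 | Weeks 8, 12, 24, 36, 52 | 5 |
| 44–71 | Weeks 12, 24, 36, 52 | 4 |
| 72–127 | Weeks 24, 36, 52 | 3 |
| 128–211 | Weeks 36, 52 | 2 |
| 212–309 | Week 52 | 1 |
| 310 onward | none | 0 |

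The Week 12 lipid value is missing only for removal by day 71, and the Week 24 value only for removal by day 127. Between the two target visits (days 86–168) there are 168 − 86 + 1 = 83 possible removal days. Week 24 is empty on 127 − 86 + 1 = 42 of them and filled by the early-withdrawal visit on 168 − 128 + 1 = 41. These count calendar days, not patients.

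**The case against.** The strongest reply is that the sentence has a narrower meaning. It speaks of harm from continuing in the study, sits in a section on early study withdrawal and comes just before the list of reasons for leaving. It may simply restate that case. But the action that triggers it is interrupting treatment, no narrower limit is written, and the best-interest reason is already listed separately.

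A second reply is that the laboratory sections are specific and sites would follow them. That is likely for the listed tests, and nothing in the documents shows a site doing otherwise. It does not help with adverse events outside those tests.

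A third reply is that the investigator who saw a threat would seldom restart. This stands in part: restart needs the investigator's agreement, rechallenge is discretionary and resumption after a CK hold is only to be considered. The lost restarts may be few.

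A reader might infer that this sentence is the only place where a health problem leads out of the study. The documents do not support that. Protocol 11.2.6 covers adverse events requiring discontinuation from the study. The Synopsis and Section 12.5 plan separate summaries of withdrawal from treatment and from the study due to adverse events, and the 10.3.1 list includes illness and adverse events. Study withdrawal for health reasons is a legitimate category; what is wrong is the automatic route into it.

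**Conclusion.** The conflict is real in the current text and worth correcting, but the exposure is limited and cannot be quantified. No rate of health-related interruption is given, and no planned conclusion is shown to change.

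A reader might take the visit-gap counts as the expected loss, or conclude that all follow-up ends for these patients. Neither follows. The counts are a worst case that assumes no later contact, although Protocol 10.3.2 and 11.2.6 may restore some, and they would fit any complete withdrawal from the study. For the key efficacy endpoints, SAP 5.3.2 already imputes missing values in off-drug patients from placebo data. ApoB and hs-CRP are not collected at visits after IMP withdrawal in any case.

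What may be lost is the option to restart or rechallenge, later scheduled safety laboratory tests, vital signs and lipids, some new non-serious adverse events, and a consistent division between study and IMP withdrawal in the disposition table. The IMP stop itself should be recorded either way. The conclusion assumes that a site reads the sentence as written.

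**What to change.** In Protocol 10.3.1, replace the sentence with: *Such patients should have IMP interrupted or stopped, and will be asked to remain in follow-up through Week 52 by clinic visit or phone. IMP may be restarted only under the restart paragraph above and Sections 11.1.6.3.1 and 11.1.6.3.4. Withdrawal from the study is reserved for the reasons listed below.* This keeps the investigator's power to end participation.

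In Protocol 10.3.2, add a clause extending the request for continued visits or calls to patients the investigator removes.

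The cost is wording in two places, made by amendment under Protocol 17.3. The visits and calls already exist in Appendix 1, and no clinical threshold for stopping or restarting IMP changes.
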